8.34 Management of Subjects with Elevations in AST, ALT and/or Bilirubin

Management of AST, ALT and/or Bilirubin Elevations	
Isolated AST/ALT elevations between 3X ULN and 8X ULN	Continue lenvatinib, but monitor weekly until AST/ALT returns to ≤ 2.5 or baseline
AST/ALT >8 X ULN	
Hold lenvatinib until AST/ALT returns to ≤ 2.5 X ULN or baseline
 
If the potential benefit of reinitiating lenvatinib treatment is considered to outweigh the risk for hepatotoxicity, then consider reintroducing lenvatinib at one dose level less and measure serum liver tests weekly for 8 weeks only after discussion with the PI
 
If AST/ALT elevations >3 X ULN recur, then lenvatinib should be permanently discontinued and patient enters event monitoring phase

AST/ALT >3 X ULN and	Discontinue lenvatinib and enter event monitoring phase

concurrent direct bilirubin elevations >2 X ULN	
Mild indirect hyperbilirubinemia, known or suspected Gilbert's syndrome, and elevation in ALT >3 X ULN	Continue lenvatinib, but monitor weekly until ALT returns to Grade 1 (NCI CTCAE v4) or baseline

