3.0 ELIGIBILITY

3.1 Inclusion Criteria

- 3.11 Age \geq 18 years.
- 3.12 Histologically or cytologically confirmed malignant secretory or non-secretory pheochromocytoma or paraganglioma that is unresectable and deemed inappropriate for alternative local regional therapeutic approaches.
- 3.13 Measurable disease as defined in [Section 11.0](#).
- 3.14 ECOG Performance Status (PS) 0, 1, or 2 ([Appendix I](#)).
- 3.15 Life expectancy $>$ 24 weeks.
- 3.16 The following laboratory values obtained \leq 14 days prior to registration.
- Absolute neutrophil count (ANC) \geq 1500/mm³
 - White blood cell (WBC) count \geq 3,000/mm³
 - Platelet count \geq 100,000/mm³
 - Hemoglobin \geq 9.0 g/dL (5.6mmol/L)
NOTE: Transfusions are not allowed \leq 7 days prior to registration
 - Total bilirubin \leq 1.5 X upper limit of normal (ULN)
(or total bilirubin \leq 3.0 X ULN with direct bilirubin \leq 1.5 X ULN in patients with well-documented Gilbert's Syndrome)
 - Aspartate transaminase (AST/SGOT) \leq 2.5 X ULN
 - Creatinine \leq 1.5 X ULN
 - Urine protein/creatinine ratio \leq 1 OR 24-hour urine protein $<$ 1.5 gram
- 3.17 Negative pregnancy test done \leq 7 days prior to registration, for women of childbearing potential only.
- 3.18 Blood pressure (BP) $<$ 150 mmHg (systolic) and $<$ 90 mmHg (diastolic). Initiation or adjustment of BP medication is permitted prior to registration provided that the average of three BP readings at a visit prior to registration is $<$ 150/90 mmHg.
- NOTE:** All patients with secretory pheochromocytoma or paraganglioma are REQUIRED to: 1) be evaluated in consultation by a hypertension specialist with specific experience in the management of hypertension in the setting of catecholamine-secreting tumors (usually an endocrinologist, nephrologist, or a cardiologist), and in the setting of hormone-associated hypertension) receive α - and β -adrenergic blockade for at least 7-14 days prior to initiation of lenvatinib (see [Appendix IV](#) for guidelines regarding proper α - and β -blockade). The hypertension specialist of record for each patient should be committed to closely following the patient during the clinical study with evaluation by said specialist required at Cycle 1 and 2 and thereafter on an as needed basis. Please see [Appendix IV](#) for guidelines on hypertension evaluation, follow up and management.
- Please note that this is a critical patient safety issue and that no exceptions to this approach are permitted.**

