⁸ AST, alk phos, total bilirubin (direct if TBili is elevated), creatinine (and calculated creatinine clearance), albumin, glucose, calcium (Ca), sodium (Na), potassium (K), magnesium (Mg), phosphorus (P), uric acid, LDH,

⁹ Urinalysis for protein, glucose, blood

¹⁰ Only if not performed previously (optional); can be performed anytime during study. Testing should include SDHD, SDHB, RET, VHL, neurofibromatosis type-1 genes.

Tests and procedures ¹	Window:				Active Treatment			End of Treatment
		≤28 days prior to registration	≤14 days prior to registration	≤7 days prior to registration	Cycle 1		Prior to Day 1 of subsequent cycles ³	
		D1	D3	D10 ²	Every 2 months			
PET-CT or CT (Chest, Abdomen and pelvis), or MRI abdomen/MRI neck, if needed	X						X	X ¹¹
ECG		X					X ¹²	
2D-ECHO	X							
Blood or Tissue- Analysis performed by Research Lab								
Optional tissue sample for correlatives (see Section 17.0) ¹³				X				
Optional research blood will be collected under IRB 13-005838 ¹⁴		X						
Quality of Life assessment								
Patient Questionnaire Booklet: EQ-5D-5L/FACT-G				X ¹⁵			X	

Cycle = 28 days

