8.0 DOSAGE MODIFICATIONS

Strictly follow the modifications in [Table 8.1](#) for the first two cycles, until individual treatment tolerance can be ascertained. Thereafter, these modifications should be regarded as [guidelines](#) to produce mild-to-moderate, but not debilitating, side effects. If multiple adverse events are seen, administer dose based on greatest reduction required for any single adverse event observed. Reductions or increases apply to treatment given in the preceding cycle and are based on adverse events observed since the prior dose.

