NOTE: Outdated or remaining drug is to be destroyed on-site per procedures in place at each institution.

15.19 **Nursing guidelines**

- 15.191 Hypertension is very common with agent. Monitor BP as per protocol and report BP elevations to the study team.
- 15.192 Diarrhea is common. This may be increased in patients who are undergoing simultaneous treatment with immunotherapy agents. Instruct patients to report any diarrhea immediately and treat symptomatically per protocol instructions.
- 15.193 Other GI side effects can occur, including decreased appetite, weight loss, and nausea/vomiting. Manage patient symptomatically and monitor for effectiveness.
- 15.194 Patients may experience fatigue. Instruct patients in energy conserving lifestyle.
- 15.195 Dermatologic related side effects have been seen, including: hand-foot syndrome, rash, and alopecia. Instruct patients to report these signs and symptoms to the study team immediately.
- 15.196 Patients may experience increased risk of bleeding. Instruct patients to report any unusual bruising or bleeding to the study team. Patients should not undergo invasive procedures without first discussing with the study team.
- 15.197 Monitor for proteinuria per protocol.

- 15.198 Rarely agent may cause decreased LVEF. Instruct patients to report any peripheral edema, DOE, chest pain or significant fatigue to the study team.
- 15.199 Monitor LFTs and renal function. Report any elevations to the provider.

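### Section 8.34 gives opposite instructions, hold and continue, for a patient with Gilbert's syndrome, mild indirect hyperbilirubinemia and ALT above 8 X ULN

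*Combined protocol and SAP*

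**What the plan says.** Section 8.34 is a four-row table for elevations in AST, ALT and bilirubin.

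- **Row 1**, isolated AST/ALT elevation between 3 X and 8 X ULN: continue with weekly monitoring.
- **Row 2**, AST/ALT above 8 X ULN: "Hold lenvatinib until AST/ALT returns to ≤ 2.5 X ULN or baseline". Restart one dose level lower is possible after discussion with the principal investigator, with weekly liver tests for 8 weeks. The row ends: "If AST/ALT elevations >3 X ULN recur, then lenvatinib should be permanently discontinued and patient enters event monitoring phase".
- **Row 3**, AST/ALT above 3 X ULN with direct bilirubin above 2 X ULN: discontinue.
- **Row 4** is triggered by "hyperbilirubinemia, known or suspected Gilbert's syndrome, and elevation in ALT >3 X ULN", where the bilirubin rise must be mild and of the indirect type. The action given is "Continue lenvatinib, but monitor weekly until ALT returns to Grade 1 (NCI CTCAE v4) or baseline".

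Such patients can be enrolled. Section 3.16 relaxes the total bilirubin limit "in patients with well-documented Gilbert's Syndrome". Row 4 is wider than that, since suspected Gilbert's syndrome is enough.

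**The concern.** Row 1 stops telling the investigator to continue once a transaminase passes 8 X ULN. Row 4 also says continue but has no such ceiling. Row 2 begins at 8 X ULN with no bilirubin condition and no carve-out for Gilbert's syndrome. Above 8 X ULN the two rows therefore overlap for a Gilbert's patient, and their actions cannot both be followed.

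One of the two literal readings errs in the unsafe direction. An investigator who takes the more specific row to override the general one would keep dosing at a transaminase level where the same table otherwise holds the drug and requires a discussion before restart. What is at stake is the safety of that patient.

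**Working it through.** No sample size, power or error rate is involved, so the check is one of logic. Take a patient with known or suspected Gilbert's syndrome, mild indirect hyperbilirubinemia, direct bilirubin not above 2 X ULN, and a measured ALT of 10 X ULN. The value 10 is only an example; any ALT above 8 X ULN gives the same result.

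1. Row 1 needs a value between 3 X and 8 X ULN. Since 10 > 8, it is not met.
2. Row 2 needs AST or ALT above 8 X ULN. Since 10 > 8, it is met: hold.
3. Row 3 needs direct bilirubin above 2 X ULN. It is not met.
4. Row 4 needs mild indirect hyperbilirubinemia, Gilbert's syndrome and ALT above 3 X ULN. Since 10 > 3, it is met: continue.

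Rows 2 and 4 both apply, with opposite actions.

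The edges of the overlap are as follows.

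- A Gilbert's patient without mild indirect hyperbilirubinemia at the time does not meet row 4, so only the hold row applies.
- A first ALT rise to between 3 X and 8 X ULN, with AST not above 8 X ULN, gives no conflict, because row 2 is not met.
- If AST/ALT in row 2 means either enzyme, AST above 8 X ULN with ALT above 3 X ULN also meets both rows. An ALT cap on row 4 would not by itself close that case.
- The conflict needs a measured ALT. The chemistry panel in the footnote to Section 4.1 reads "AST, alk phos, total bilirubin (direct if TBili is elevated), creatinine (and calculated creatinine clearance), albumin" and goes on without naming ALT. The nursing guidelines in Section 15.19 say only "Monitor LFTs and renal function. Report any elevations to the provider". Section 8.34 nevertheless assumes that ALT is available.

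Next, does other text rank the two rows?

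- **Section 8.0** takes the greatest reduction when several adverse events occur. Here one ALT value meets two rows, and the choice is between holding and continuing, not between two dose reductions.
- **Section 7.2** calls for medical judgment on events of grade 2 or higher. It names no row, and AST and ALT are not among its listed criteria.
- **Section 7.6** ends treatment for unacceptable adverse events or on the investigator's judgment. It permits stopping but does not choose between the rows.
- **Section 8.2** has a residual row for other non-hematologic events: hold at grade 3, discontinue at grade 4. The documents do not print the CTCAE cut-offs for ALT, and nothing says this residual row outranks a table written specifically for AST and ALT.

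All four lean towards caution or leave room for it. None settles which row applies.

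**The case against.** The strongest reply is that a sensible investigator would hold. Rows 3 and 4 look like a pair that separates direct from indirect bilirubin, which leaves row 2 to govern everyone above 8 X ULN. Sections 8.0, 7.6 and 8.2 point the same way. Patients are treated only at Mayo Clinic (Section 7.5), and restart after a hold already requires the principal investigator. Much of this stands. Holding is the sensible reading, and divergent handling between sites is not a demonstrated problem. But that reading is not written down, and row 4, with three conditions against one, can fairly be taken as the specific exception.

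Some stronger readings are tempting but not supported.

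- A reader might infer that the protocol forces dosing at any ALT level. It does not: Section 7.6 always allows the investigator to stop, and the residual row in Section 8.2 calls for a hold or discontinuation at grades 3 and 4.
- A reader might infer that Section 8.34 is binding early and loose later, because Section 8.0 requires strict adherence "for the first two cycles, until individual treatment tolerance can be ascertained". That sentence names Table 8.1, the dose-level table, and not 8.34.
- A reader might try to size the problem from Section 15.17, which lists increased ALT among events below 1%. That list also contains proteinuria, stomatitis and decreased weight, which Section 1.233 reports at 31%, 36% and 46% in the phase 3 thyroid cancer trial. It cannot serve as a cap on a laboratory event rate, and it gives no rate for ALT above 8 X ULN.

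**Conclusion.** The contradiction is real and can be confirmed from Section 8.34 alone: for the patient described, one row says hold, another says continue, and no text ranks them. Severity is minor.

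The situation is rare, because several conditions must coincide, but it cannot be quantified. The documents give no rate of ALT above 8 X ULN, no proportion of patients with Gilbert's syndrome and no share of those with mild indirect hyperbilirubinemia at the relevant time. The conclusion rests on ALT actually being measured and on the rows being read literally.

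The consequence is limited to individual patient safety. A reader might infer that the trial's result is at risk; it is not. The two-stage design, the confirmed response endpoint and the planned analyses do not depend on this row.

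**What to change.** Two changes to Section 8.34:

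1. In the Gilbert's row, bound the trigger on both sides: *ALT above 3 X ULN and up to 8 X ULN*.
2. Under the table, add: *The row for AST/ALT above 8 X ULN applies to all patients, including those with Gilbert's syndrome.* This also covers the case where AST, not ALT, is above 8 X ULN.

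One matter stays outside this fix. After a hold and restart, row 2 requires a permanent stop if AST/ALT above 3 X ULN recurs, while row 4 could tell the same patient to continue. Whether the permanent stop should apply to Gilbert's patients is a clinical decision for the sponsor, and the documents do not show which was intended.

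The cost is one row edit and one sentence in a protocol amendment, with no change to sample size, endpoint or test schedule. The downside is that a rare Gilbert's patient may be held where the current row would allow treatment to continue.

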8.35 Management of Other Adverse Events

CTCAE SOC	Adverse Event	Grade	Treatment Modification
Respiratory, thoracic and mediastinal disorders	Broncho-pulmonary hemorrhage	Grade 1	Hold therapy if hemoptysis is in excess of 2.5 mL (1/2 teaspoon) per day until resolved, otherwise maintain current dose.
		Grade 2	Hold lenvatinib unless resolved to \leq Grade 1; reduce dose to next lower dose level, and continue treatment. If Grade 2 or greater hemorrhage/ bleeding recur following dose reduction, discontinue lenvatinib and patient enters event monitoring phase
		Grades 3 or 4	Discontinue lenvatinib and patient enters event monitoring study phase
Vascular disorders	Thrombo-embolic event	Grade 1	No interruption in treatment; maintain current dose
		Grade 2, 3	Hold lenvatinib until subject is receiving a stable dose of Low Molecular Weight Heparin (LMWH). Concurrent warfarin will not be allowed, if patient needs warfarin, stop the study drug and enter event monitoring. Treatment may resume during the period of full-dose anticoagulation if all of the following criteria are met: 
• The subject must be have been treated with an anticoagulant at the desired level for at least one week• The subject must not have had a Grade 3 or 4 or significant Grade 2 hemorrhagic event while on anticoagulant Subject should be monitored as clinically indicated during anticoagulation treatment and after resuming study treatment.
		Grade 4 or pulmonary embolus	Discontinue lenvatinib and patient enters event monitoring

9.0 ANCILLARY TREATMENT/SUPPORTIVE CARE

9.1 Full supportive care

Patients should receive full supportive care while on this study. This includes blood product support, antibiotic treatment, and treatment of other newly diagnosed or concurrent medical conditions. All blood products and concomitant medications such as antidiarrheals, analgesics, and/or antiemetics received from the first day of study treatment administration until 30 days after the final dose will be recorded in the medical records.

9.2 Blood products and growth factors

Blood products and growth factors should be utilized as clinically warranted and following institutional policies and recommendations. The use of growth factors should follow published guidelines of the Journal of Clinical Oncology, Vol 24, No 18 (June 20), 2006: pp. 2932-2947.

9.3 Antiemetics

Antiemetics may be used at the discretion of the attending physician.

9.4 Diarrhea

Diarrhea could be managed conservatively with loperamide. The recommended dose of loperamide is 4 mg at first onset, followed by 2 mg every 2-4 hours until diarrhea free (maximum 16 mg/day).

In the event of Grade 3 or 4 diarrhea, the following supportive measures are allowed: hydration, octreotide, and antidiarrheals.

If diarrhea is severe (requiring intravenous rehydration) and/or associated with fever or severe neutropenia (grade 3 or 4), broad-spectrum antibiotics must be prescribed. Patients with severe diarrhea or any diarrhea associated with severe nausea or vomiting **should be hospitalized** for intravenous hydration and correction of electrolyte imbalances.

9.5 Hypertension

Please see Appendix IV for guidelines regarding management of hypertension. They should be seen by an expert in management of hypertension before they are started on the study drug. During the therapy patients will experience worsening of hypertension especially the secretory tumors and repeat consultation with the expert in recommended for concurrent management.

9.6 Tumor lysis syndrome

Patients may experience tumor lysis-like syndrome if they get profound, rapid response to therapy. Tumor lysis is characterized by hyperkalemia, hypocalcemia, elevated uric acid, renal failure and ECG abnormalities. Please see [Section 8.2](#) for dose modification. If there are changes in the electrolytes they should be managed as per the [Section 8.31](#). If there is suspicion of tumor lysis or tumor lysis-like syndrome then therapy should be held, Allopurinol 300 mg daily should be instituted. EKG, laboratory examination, history and physical examination should be repeated in 1 week. If EKG and laboratory values have normalized, and patient is clinically stable then therapy can be re-instituted.

9.7 Precautions/Warnings

9.71 Drug-Drug Interactions

There have been few completed human studies, at present, specifically evaluating drug-drug interactions with lenvatinib. The weak inhibitory effect on CYP P450

enzymes (in vitro) exhibited by lenvatinib suggests a low risk of lenvatinib interference with the pharmacokinetics of other drugs coadministered in usual clinic practice (Shumaker, Aluri et al. 2015). However, preliminary preclinical studies identify CYP3A4 as an important enzyme responsible for human hepatic metabolism of lenvatinib. Caution should be exercised when administering drugs metabolized by CYP3A4 or drugs that are inhibitors or inducers of CYP3A4 (including herbal supplements or grapefruit), as administration of such drugs could affect the metabolism of lenvatinib. Please refer to [Appendix III](#). Other medications have potential to increment risks to patients when combined with lenvatinib. These include: i) agents that increase bleeding risks (Warfarin is specifically prohibited, whereas heparin and NSAIDS/anti-platelet agents should be used with caution), and ii) bisphosphonates and denosumab (as there is potential that combined therapy with lenvatinib may further increase the risks of jaw osteonecrosis and other bone liabilities due to combined antiangiogenic effects).

9.72 Hypertension

Hypertension is an important AE associated with lenvatinib (Schlumberger, Tahara et al. 2015). Frequent blood pressure (BP) monitoring is important in subjects receiving lenvatinib. In addition patients with secretory pheochromocytomas and paragangliomas are at risk for hypertension and hypertensive crisis by virtue of disease. Patients will be provided with a diary in which to record their daily BP readings (see [Appendix VI](#)) for first three cycles. Daily readings should be taken. If the systolic reading is >140 mmHg OR the diastolic reading is >90 mmHg OR any combination of elevated systolic and diastolic readings, patients will be instructed to retake their blood pressure within 1-4 hours. If a second consecutive reading is elevated patient will be instructed to contact their physician as soon as possible. Patients should seek medical advice if their BP exceeds 180 mmHg (systolic) or 105 mmHg (diastolic) at any time and should also be encouraged to contact their physician if they are concerned about any symptoms that may be associated with high BP (e.g., headache). In addition, expert consultation and follow-up for patients with secretory tumors will be required prior to enrollment, and during the study. Experience to date suggests that increases in BP may occur following dosing with lenvatinib for a number of weeks and that these increases may occur relatively quickly. It is imperative that the investigator institute appropriate measures to control BP. This may necessitate changes to existing antihypertensive medication, addition of new medication(s) and/or holding therapy with lenvatinib. Considering the potential of this adverse event we will monitor patients closely in the initial weeks with frequent measurement of blood pressure in clinic on Day 1, 3 and 10.

Recommendations for hypertension monitoring and management are presented in [Appendix IV](#).

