4.0 STUDY CALENDAR

4.1 Test Schedule

Tests and procedures ¹				Active Treatment				End of Treatment	
	≤28 days prior to registration	≤14 days prior to registration	≤7 days prior to registration	Cycle 1			Prior to Day 1 of subsequent cycles ³	Every 2 months	
				D1	D3	D10 ²			
Tests and procedures ¹	Window:						±3 days	±7 days	±14 days
Clinical Procedures									
Vital signs, history (including personal/family history for prolonged QTc) and exam, weight, PS		X		X	X	X	X		X
Height		X							
Review of concurrent medications ⁴		X					X		
Pregnancy test ⁵			X						
Blood pressure monitoring ⁶		X		X	X	X	X		
Adverse event assessment		X		X	X	X	X		X
Consultation with endocrinologist, cardiologist, or nephrologist for blood pressure management		X					X		
Hematology: CBC/diff ⁷		X					X		X
Chemistry Panel ⁸		X					X		X
TSH		X					X		
24 hr urine catecholamine and metanephhrines		X					X		
Plasma fractionated metanephhrines		X					X		
Urinalysis ⁹		X					X		
Urine protein/creatinine ratio		X					X		
Genetic counseling and testing at discretion of patient and counselor ¹⁰	X								

¹ All tests and procedures are clinically indicated, unless noted with an R to indicate funding by research

² May be omitted at discretion of treating provider and replaced with telephone call contact.

³ If patient is tolerating treatment well, return visits may be performed over the phone for non-imaging cycles (starting with cycle 3, 5, 7 etc.). During these phone visits the patient status, treatment information, and Adverse Event Assessments must be assessed and recorded. Labs may be done locally and transmitted to Mayo Clinic.

⁴ Concurrent/concomitant medications are reviewed every cycle. Only requested medications are recorded in the study case report forms.

⁵ For women of childbearing potential only. Must be done ≤7 days prior to registration

⁶ Note: 1) daily monitoring of blood pressure is REQUIRED and must be recorded in patient diaries throughout the entire duration of therapy; 2) any systolic BP >150 mm Hg and/or diastolic BP >100 mm Hg must be brought to the attention of treating provider <24h after noted; 3) any systolic BP >200 mm Hg and/or diastolic BP >110 mm HG should prompt immediate cessation of lenvatinib therapy maintained until remediation to <150 mm Hg systolic is accomplished.

⁷ Must include: hemoglobin (hgb), MCV, leukocyte count, neutrophils (ANC), monocyte count, lymphocyte count, and platelet count (PLT)

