Appendix VI Patient Blood Pressure Diary

Today's date _____

Patient Initials _____

Patient Study ID _____

INSTRUCTIONS TO THE PATIENT:

1. Your blood pressure readings have two numbers. The first number is the pressure in your blood vessels during a heartbeat (systolic), and the second number is the pressure in the vessels when the heart rests in between beats (diastolic). These numbers are usually written with a slash in between them (for example, 110/85).
2. Record the date, then record your blood pressure once daily:
3. If you take your blood pressure at other times of the day, please record the numbers and time under "Other readings".
4. Normal blood pressure is usually considered to be 120/80 mmHg. If your systolic pressure is greater than 140 or your diastolic blood pressure is greater than 90 when you measure your blood pressure. Repeat your blood pressure within 1-4 hours. If your blood pressure is still elevated please contact your doctor's office at [REDACTED] for instructions. Also, you should contact your doctor's office at any time your blood pressure exceeds 180 mmHg (systolic) or 105 mmHg (diastolic), or at any time you have symptoms that you think may be related to hi blood pressure (examples include headache, nausea, vomiting, confusion, anxiety, restlessness). If you need to call after business hours or during holidays or weekends, please call [REDACTED] and ask for the Medical Oncologist on call.
5. Please bring this form to your visit at the end of Cycle 1, 2 and 3.

Date	Blood Pressure readings	Other readings (include time of day)	Date	Blood Pressure readings	Other readings (include time of day)
	/			/	
	/			/	
	/			/	
	/			/	
	/			/	
	/			/	
	/			/	

Date	Blood Pressure readings	Other readings (include time of day)	Date	Blood Pressure readings	Other readings (include time of day)
	/			/	
	/			/	
	/			/	
	/			/	
	/			/	
	/			/	
	/			/	
	/			/	
	/			/	
	/			/	
	/			/	
	/			/	
	/			/	
	/			/	
	/			/	
	/			/	
	/			/	
	/			/	
Patient's Signature: _____					
Date: _____					
Physician's Office will complete this section:					
Date of this clinic visit		Physician/Nurse/Coordinator's Signature			

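### The study calendar requires a blood pressure diary for all of therapy and 24-hour notice above 150/100; Section 9.72 and the patient form provide for three cycles and let some of those readings go unreported

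*Combined protocol and SAP*

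**What the plan says.** **Study calendar (Section 4.1, footnote 6).** Three rules apply to home blood pressure (BP):

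- Recording: "daily monitoring of blood pressure is REQUIRED and must be recorded in patient diaries throughout the entire duration of therapy".
- Notice: "any systolic BP >150 mm Hg and/or diastolic BP >100 mm Hg must be brought to the attention of treating provider <24h after noted". No repeat reading is needed first.
- Stopping: "any systolic BP >200 mm Hg and/or diastolic BP >110 mm HG should prompt immediate cessation of lenvatinib therapy", kept up until systolic pressure is back below 150.

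**Section 9.72.** The diary is provided "for first three cycles. Daily readings should be taken. If the systolic reading is >140 mmHg OR the diastolic reading is >90 mmHg". A reading at that level is to be retaken in 1-4 hours, and the physician is contacted if the second reading is also raised. Separately, the patient seeks advice above 180 systolic or 105 diastolic at any time, and is encouraged to call about symptoms.

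**Appendix VI (the form the patient holds).** Item 4 gives the same sequence: "Repeat your blood pressure within 1-4 hours. If your blood pressure is still elevated please contact your doctor's office". It adds calls "at any time your blood pressure exceeds 180 mmHg (systolic) or 105 mmHg (diastolic" and "or at any time you have symptoms that you think may be related to hi blood pressure". Item 5 reads: "Please bring this form to your visit at the end of Cycle 1, 2 and 3".

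**Appendix IV.** D.1 (non-secretory tumors) states that decisions to hold or reduce lenvatinib must rest on readings taken in the clinic by a medical professional. D.2 (secretory tumors) has no such rule. In both, persistent hypertension means qualifying elevations on at least two measurements 7 or more days apart.

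**The concern.** The calendar and the patient-facing text conflict on two points: how long the diary runs, and which home readings must be reported. A third, narrower conflict applies to non-secretory tumors only. Footnote 6 calls for immediate cessation above 200 and/or 110, while D.1 bars hold decisions that are not based on clinic readings, so a provider phoned about such a home reading has two rules.

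This matters because hypertension is the risk the protocol is built around. Section 1.233 reports it in 68% of patients in the phase 3 thyroid trial, grade 3 or worse in 42%. Section 1.3 lowers the starting dose to 20 mg because of it.

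The diary also lapses at an awkward time. Section 8.1 allows escalation to 24 mg after two tolerated cycles, so the diary covers at most one cycle at the higher dose. Calendar footnote 3 allows phone visits in non-imaging cycles from cycle 3, and Section 7.4 lets visits drop to every 56-60 days.

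A patient who follows the form to the letter can therefore leave a mandatory notice ungiven. After cycle 3, the daily home record is required by one text but not provided for by the other.

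**Working it through.** The plan states no figure on this point, so the check compares the two rules and then counts days.

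**1. Notice rule.** Let S1/D1 be the first reading and S2/D2 the repeat, with no symptoms.

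- Footnote 6: notify if S1 > 150 or D1 > 100.
- Section 9.72 and Appendix VI: call if S1 > 180 or D1 > 105; otherwise, if S1 > 140 or D1 > 90, repeat, and call if S2 > 140 or D2 > 90.

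The two rules were compared over every whole-number first reading from 90 to 220 systolic and 50 to 130 diastolic:

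| First reading | Repeat | Footnote 6 | 9.72 / Appendix VI |
|---|---|---|---|
| 141-150 or 91-100 | still > 140 or > 90 | no notice | call |
| 151-180 or 101-105 | still > 140 or > 90 | notice | call |
| 151-180 or 101-105 | 140/90 or below | **notice** | **no call** |
| > 180 or > 105 | any | notice | call |

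The form falls short of the footnote only in the third row. The bands are 151-180 when systolic pressure alone triggers the footnote and 101-105 when diastolic pressure alone does. If the repeat is still high there is no gap. In the first row the form is the stricter text.

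**2. Diary duration.** Inputs: 28-day cycles and a 5-year maximum (Section 7.1); diary for three cycles (Section 9.72, Appendix VI); response judged within six cycles (Sections 16.121 and 16.122).

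- Days provided for: 3 × 28 = 84.
- Response window: 6 × 28 = 168 days; 84/168 = 50%, leaving 168 − 84 = 84 days.
- Five-year maximum: 5 × 365.25 ≈ 1826 days; 1826/28 ≈ 65.2 cycles; 84/1826 = 4.6%, leaving 1826 − 84 = 1742 days.

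**3. Persistence rule.** One settled reading does not meet the Appendix IV definition. Read literally, two settled readings of 160-180 systolic a week apart in a secretory patient could meet the grade 3 hold row of D.2, yet neither would prompt a call. This shows that the gap can touch a dosing rule; it does not show how often.

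**4. Readings above 200/110.** These already exceed 180/105, so the form prompts a call. The absence of a stop level on the form is an omission, not a contradiction. The contradiction lies between footnote 6 and D.1, in what the provider may then do.

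**The case against.** The strongest reply is that other safeguards leave little exposed.

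- The calendar schedules BP monitoring and a BP-management consultation before each subsequent cycle, and Section 10.61 has hypertension graded at every evaluation.
- Secretory patients must see a hypertension specialist at cycles 1 and 2 (Section 3.18).
- Section 9.72 puts clinic BP checks on days 1, 3 and 10, although the day 10 visit may be replaced by a call.
- In cycles 1-3 a settled reading is still written down and seen when the diary comes back.
- Section 9.72 asks for daily readings without telling anyone to stop, so what lapses is the supply and return of the form, not necessarily the measuring.

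All of that stands, and it limits the harm. It does not remove the conflict: a diary returned at the end of a cycle does not meet a 24-hour notice, and per-cycle checks do not replace a required daily record.

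The secretory example in step 3 is hypothetical and should carry little weight. The five-year cap is a ceiling, not expected exposure, and the six-cycle window is for judging response. Both percentages describe diary supply only.

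On D.1, stopping at once and confirming in clinic would be a sensible reconciliation, but the text does not say so.

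Finally, relaxing footnote 6 to match Section 9.72 would also remove the duration and threshold conflicts. The documents do not dictate the direction; the stricter text is preferred here on safety grounds. It is also true that footnote 6's restart level (systolic below 150) differs from Appendix IV's (at or below 159/99). That is a separate conflict.

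**Conclusion.** The inconsistency holds and should be fixed. Footnote 6 and the text and form the patient follows cannot both be met, and nothing ranks them.

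The diary is provided for 84 days, against a requirement that runs as long as treatment does: half of a six-cycle stay, or 4.6% of the five-year maximum. The notice gap is confined to single asymptomatic readings of 151-180 systolic or 101-105 diastolic that settle to 140/90 or below. Its frequency cannot be computed from the documents. The hold-rule conflict above 200/110 affects non-secretory patients only.

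The conclusion assumes that footnote 6 covers home readings, which its diary wording supports. Sample size, error rates and the primary endpoint are unaffected.

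**What to change.** - **Section 9.72 and Appendix VI item 5:** issue the diary for every cycle on lenvatinib and collect it each cycle, or at the next in-person visit when a cycle visit is by phone.
- **Section 9.72 and Appendix VI item 4:** keep the repeat-and-call rule above 140/90, and add an instruction to call within 24 hours for any reading above 150 systolic or 100 diastolic, even if the repeat is lower.
- **Appendix IV D.1:** exempt readings above 200 systolic or 110 diastolic from the clinic-reading rule, so that the provider holds lenvatinib at once as footnote 6 requires. The same edit is a good place to settle the restart level.

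A self-stop line on the patient form is optional. The cost is protocol wording and a reprinted form. The downsides are more diary pages, some extra calls, and an occasional dose held for a false home reading.
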